2.1 Change in planned analyses from the protocol

The protocol specifies that analyses are to be conducted by "patient group" which is formed by the types of cancer at study entry. That is, subjects with the same tumor type will be considered as in the same "patient group". For efficacy analyses, with exception of the primary analysis of clinical benefit rate (i.e., summarized by 'patient group'), other descriptive summaries in general will be produced overall for all ceritinib-treated subjects. Separate summaries may be produced for those groups with at least 10 subjects. All subjects will be combined for any safety analyses.

[figure not shown]
In the event of a low response rate, DOR will only be listed, and not tabulated. Subjects who had no disease progression/death will be censored at last adequate tumor assessment on or before the discontinuation/completion of the study.

For determination of PFS events, due to tumor assessments post study treatment are not collected, deaths occurred more than 30 days post treatment without prior progressive disease/relapse of disease will not be considered as an event.

For overall survival analysis, no KM method will be used due to early study termination. Descriptive summaries will be provided instead.

For vital signs, values will be descriptively summarized by nominal visit. Separate summaries of significant abnormalities will not be provided, but will be reflected in adverse events (AEs).

For cardiac imaging, due to data collection is only as clinically indicated, thus only listing will be provided.

3 Subjects and treatments

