10.5.2 Other secondary efficacy objectives

The secondary objectives of the study:

- To assess progression free survival (PFS) based on local investigator assessment per RECIST 1.1 or other appropriate hematological response criteria
- To assess overall survival
- To assess duration of response (DOR) based on local investigator assessment per RECIST 1.1 or other appropriate hematological response criteria
- To assess safety and tolerability

The secondary efficacy variable progression free survival (PFS) is defined as the time from the date of first dose to the date of first documented disease progression or relapse or death due to any cause.

PFS will be summarized and graphed using the Kaplan-Meier product-limit method for the entire study cohort. For cohorts with at least 10 subjects, separate PFS analyses will be conducted for each cohort. Patients who drop-out without progression will be censored at the time of last adequate assessment. The estimates of the 25th, median, 75th percentiles of the PFS and their 95% confidence intervals will be provided, if applicable.

Overall survival (OS) is defined as the time from the date of first dose to the date of death due to any cause. If a patient is not known to have died, survival time will be censored at the date of the last contact.

OS will be summarized and graphed using the product-limit method as above.

The duration of response applies only to patients whose best response was PR or CR. For patients with solid tumors the assessment criteria will be RECIST 1.1 and will include responses of CR and/or PR. For hematologic tumors other appropriate hematological response criteria will apply and are included in the appendices. The duration of response is defined as the time from the first documented response to the date first documented disease progression or relapse or death due to any cause. The duration of response will be summarized descriptively for the entire study cohort.

If the study primary efficacy endpoint is not met, Novartis may decide not to conduct some of the above secondary efficacy analyses but instead provide those endpoints in listings only.

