6.3 Progression Free Survival (PFS)

PFS is defined as the time from the date of first dose of ceritinib to the date of the first documented disease progression/relapse or death due to any cause within 30 days of the last dose, and is calculated as $PFS = (\text{date of progression/relapse or death} - \text{date of first study treatment} + 1)$. Disease progression noted as the reason for discontinuation of treatment will be considered as a progression, thus will be considered as an event for PFS.

Subjects who discontinue or complete study treatment without disease progression will be censored at last adequate tumor assessment on or before the discontinuation/completion of the study. If there is no tumor assessment for the subject, the PFS will be censored at Day 1.

PFS will be summarized and graphed using the Kaplan-Meier product-limit method¹. The estimated median survival time, the corresponding 95% CIs², and 25th and 75th percentiles will be provided. In addition, survival rate estimates at 1, 2, 3, 4, 5, 6, and 12 months with 95% CIs will also be provided. For cohorts with at least 10 subjects, separate PFS analyses will be conducted for each cohort.

The above analyses will be performed for the FAS.

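### The SAP's PFS leaves out recorded deaths more than 30 days after last dose and never reports the protocol's any-cause PFS; the effect can go either way

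*SAP*

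**What the plan says.** Protocol 10.5.2 (and Table 3-1) measures PFS from first dose to "first documented disease progression or relapse or death due to any cause". No window is placed on death. The same section adds: "Patients who drop-out without progression will be censored at the time of last adequate assessment". Protocol 10.4.4 applies cut-off censoring to patients who have neither progressed nor died.

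SAP 6.3 accepts only "death due to any cause within 30 days of the last dose". Patients who stop without progression "will be censored at last adequate tumor assessment on or before the discontinuation/completion of the study", or at Day 1 if they have no tumor assessment. SAP 2.1 lists this among the changes from the protocol: "deaths occurred more than 30 days post treatment without prior progressive disease/relapse of disease will not be considered as an event". It gives the reason: "due to tumor assessments post study treatment are not collected". SAP 6.3 also provides that "Disease progression noted as the reason for discontinuation of treatment will be considered as a progression".

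All deaths are still counted under overall survival (SAP 6.4) and listed (SAP 7.2). SAP 6.3 plans Kaplan-Meier PFS overall and for each cohort of at least 10 subjects. Neither document plans a PFS sensitivity analysis.

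**The concern.** Once a patient stops treatment without progression, scanning ends (Protocol 7.1.2) and efficacy follow-up is marked not applicable (Protocol 7.1.4.2). Apart from any end-of-treatment scan, death is then the only PFS event that can still be seen. The SAP treats a known death after day 30 as if the patient had been event-free and lost at the last scan. If patients who stop for toxicity or by choice differ in prognosis from those who stay on treatment, that censoring is informative.

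The same death would count in one output and be censored in another, and the endpoint the protocol defines would not appear in the report. A reader could not correct for this, because the SAP does not plan to say how many deaths the rule removes.

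**Working it through.** There is no planned PFS figure to reproduce: the SAP states no power consideration for secondary objectives and gives no expected number of PFS events. The check therefore compares the texts, then tests the direction of the effect.

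**1. Who is affected.** Progression recorded as the reason for stopping is a PFS event, and SAP 3.2 allows that reason on clinical as well as radiological grounds. The rule therefore reaches only patients who stop for another reason, have no prior progression and die more than 30 days after last dose.

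**2. The window.** Scans are due every 8 weeks, or 56 days. For a patient who stops just after a scan, a death on days 31 to 56 falls before the next scan would have been due, yet is dropped. Thirty days matches the safety follow-up (Protocol 7.1.4.1), not the disease-assessment schedule.

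**3. Direction, hand example (invented data).** Nine patients have events at months 1, 2, 3, 4, 5, 6, 7 and 10, and one censoring at month 12. A tenth stops without progression, has a last scan at month 2 and dies at month 8, more than 30 days after last dose.

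- Protocol rule: S(6) = 4/10 = 0.400; S(8) = 2/10 = 0.200.
- SAP rule: after month 2, S = 0.8 with 7 at risk. S(6) = 0.8 × 6/7 × 5/6 × 4/5 × 3/4 = 0.8 × 3/7 = 0.343. S(7) = 0.8 × 2/7 = 0.229, which still holds at month 8.

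The SAP curve is lower at month 6 and higher at month 8.

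**4. Why the sign changes.** Under a constant hazard, let the SAP rule give e events over exposure E. Let d deaths be dropped, each on average x months after its last scan. The SAP hazard is e/E and the protocol hazard is (e + d)/(E + dx). They are equal when x = E/e, which is the mean PFS, whatever d is. A shorter gap means the SAP rule lengthens PFS; a longer gap means it shortens it. With mean = median/ln 2, assumed medians of 2, 4 and 6.9 months put the break-even gap at 2.9, 5.8 and 10.0 months.

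**5. Simulation (200,000 patients per scenario, 24-month cut-off).** Only the 8-week scans and the 30-day window come from the plan. Assumed ranges: median PFS 2, 4 or 6.9 months; 10, 25 or 40% stopping without progression. Two anchors from the earlier ceritinib study lie in these ranges: 10.2% stopping for adverse events and a median PFS of 6.90 months in previously ALK-inhibitor-treated lung cancer.

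| SAP minus protocol PFS | 6 months | 12 months |
|---|---|---|
| Progression precedes the late death (54 scenarios) | −0.216 to +0.001 | −0.133 to +0.051 |
| Late death is itself the first event (27 scenarios) | −0.131 to +0.037 | −0.059 to +0.057 |

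Two contrasting cases from the second row, both with 25% stopping without progression:

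- Median PFS 6.9 months, death a median of 1 month after stopping: 6-month PFS is 0.519 (SAP) against 0.496 (protocol), and 12-month PFS is 0.267 against 0.233.
- Median PFS 2 months, death a median of 4 months after stopping: 6-month PFS is 0.115 (SAP) against 0.187 (protocol).

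**The case against.** The strongest defence is that the protocol rule is not an unbiased reference. With no scans after treatment, counting a late death as the event dates an unseen progression at that death. In the scenarios where progression comes first, the protocol rule overstated 6-month PFS by 0.003 to 0.218 relative to continued 8-week scanning. The SAP rule's error there ran from −0.052 to +0.088. This stands, and it is why the two versions belong side by side rather than one simply replacing the other.

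It can also be said that Protocol 10.5.2 already censors drop-outs at the last adequate assessment. That sentence is silent on later death, however. Read with the event definition and with 10.4.4, a patient known to have died before cut-off is not a censored patient.

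Other points that stand: the change is openly declared; Table 7-1 footnote 3 requires an end-of-treatment scan in some cases; patients who withdraw consent leave survival follow-up; and that follow-up closed on 4 August 2016, so late deaths are only partly observed.

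A reader might infer that dropping deaths must bias PFS upward, for example by going from 67 events to 60 at fixed exposure and reading off a median longer by 67/60 = 1.12. The documents do not support this. Those event counts are not in them, and the sum corresponds to x = 0 in step 4, whereas every dropped death falls more than 30 days after last dose.

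**Conclusion.** The departure from the protocol's definition is real and its stated reason covers only part of it. The censoring may be informative, and neither its direction nor its size can be determined from the documents, which do not report how many patients stopped without progression or died after day 30.

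Under the assumed inputs the effect ranges from negligible to material. With 10% stopping without progression, median PFS 6.9 months and unchanged prognosis after stopping, the two rules differ by less than 0.01 at 6 months. With more stopping, the difference is larger and of either sign. In a cohort near the 10-subject threshold, a single death can change a reported rate by several percentage points, as step 3 shows.

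The consequence is limited. PFS is a descriptive secondary endpoint in a single-arm study and does not enter the clinical benefit success rule. This is a worthwhile, inexpensive improvement to reporting, not a threat to the trial's main conclusion.

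**What to change.** Report Kaplan-Meier PFS under the protocol definition, with all recorded deaths without prior progression as events, next to the SAP's 30-day version. Do so overall and for each cohort of 10 or more, label both clearly, and state how many deaths are classified differently.

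The cost is one extra analysis of data already collected. There are two limits to state with it. Some deaths will fall long after the last scan, so the all-deaths curve can date unseen progression late. Deaths after survival follow-up closed on 4 August 2016 are not observed under either rule.

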10.4.4 Handling of missing values/censoring/discontinuations

A patient who has not progressed or died at the date of the analysis cut-off would have his/her PFS and OS censored at the time of the last adequate assessment before the cut-off date. Any disease assessment indicating response status other than “unknown” or “not done” is considered an adequate response assessment.

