The primary efficacy objectives of the study, clinical benefit (definition details see Section 6.1) associated with ceritinib treatment based on local investigator assessment, will be summarized. The clinical benefit rate will be analyzed using a Bayesian hierarchical model to evaluate trial success and futility, and the relationship between relevant pathway regulation and the response to treatment with ceritinib (if applicable). Analysis details are documented in Section 10.

Duration of response (DOR) based on local investigator assessment will be analyzed. In the event of a low response rate, DOR will be listed only without frequency summaries. Overall response (OR) will be summarized with the number and percentages of subjects for each response category (e.g., for solid tumor - CR, PR, SD, PD, Not evaluable). Progression-free survival (PFS) will be summarized using Kaplan-Meier (KM) methodology. Due to limited survival follow-up for the study, overall survival will only be descriptively summarized, ie, only the frequency of deaths will be provided.

Subject demographics, disease characteristics (including mutation analyses), ceritinib treatment, and safety variables will be summarized descriptively, by nominal visit (if applicable), and/or overall.

Data used for the analyses specified in this document will come from the Electronic Data Capture (EDC) system. In addition, the mutation data from the central laboratory will be collected in an Excel spreadsheet format and subsequently be uploaded to a secure FTP site by Novartis.

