6.4 Overall Survival (OS)

Due to limited overall survival follow-up, only the number and percentage of all deaths will be presented.

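### Overall survival is reduced to a crude death percentage that depends on accrual and closure date; the protocol's Kaplan-Meier analysis should be kept

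*SAP*

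**What the plan says.** Protocol section 10.5.2 makes OS a secondary endpoint, measured from first dose to death from any cause. Its censoring rule is "If a patient is not known to have died, survival time will be censored at the date of the last contact", and its method is "OS will be summarized and graphed using the product-limit method as above".

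The SAP drops the method in three places. Section 2.1, which lists departures from the protocol, says "For overall survival analysis, no KM method will be used due to early study termination". The overview in section 2 says "overall survival will only be descriptively summarized, ie, only the frequency of deaths will be provided". Section 6.4 says "Due to limited overall survival follow-up, only the number and percentage of all deaths will be presented". The stated reasons are early termination and limited follow-up.

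SAP section 2 gives 4 August 2016 as the date on which survival follow-up was closed. The plan had been to collect survival every 3 months until 2 years after the last enrolment. SAP section 6.3 keeps Kaplan-Meier for progression-free survival (PFS), with rates at 1 to 6 and 12 months.

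Protocol section 10.4.4 gives a second censoring rule: a patient without progression or death at the cut-off "would have his/her PFS and OS censored at the time of the last adequate assessment". An adequate assessment there means a disease response assessment, not a survival contact.

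**The concern.** Stopping follow-up on one calendar date leaves patients with different lengths of observation, because they entered at different times. Kaplan-Meier was designed for that situation. A crude percentage counts a patient followed for 2 months and one followed for 20 months alike, so it mixes survival with the accrual pattern and the closure date.

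The stake is how well a stated secondary endpoint can be read. OS is also the only time-to-event endpoint that can count late deaths: SAP sections 2.1 and 6.3 exclude from PFS any death more than 30 days after treatment without prior progression. Those deaths would appear only as part of a total, without their timing.

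**Working it through.** **1. Nothing to reproduce.** The documents give no OS event count, survival rate or power. SAP section 9 says that no power was considered for secondary objectives. What follows is illustration under stated assumptions.

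**2. Inputs.**
- From the documents: accrual of up to 2 years (protocol appendix Q, Trial Logistics; SAP section 10.1.2); a primary report cut-off once all patients could have had 16 weeks of treatment, about 4 months (protocol section 4.2); 70 to 90 patients planned (protocol section 5.1).
- Assumed: exponential OS with median 6, 10 or 14 months; follow-up uniform between a and b months.

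**3. Formulas.** λ = ln 2 / median. Twelve-month mortality = 1 − exp(−12λ). Expected crude death fraction = 1 − [exp(−λa) − exp(−λb)] / [λ(b − a)].

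**4. One case in full, median 10 months.** λ = 0.0693, so 12-month mortality = 1 − 0.435 = 56.5%.
- Follow-up 2 to 14 months: 1 − (0.871 − 0.379)/0.832 = 40.9%.
- Follow-up 4 to 28 months (24 months of accrual plus 4): 1 − (0.758 − 0.144)/1.664 = 63.1%.

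**5. All cases.**

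| Median OS (months) | 12-month mortality | Crude deaths, follow-up 2–14 months | Crude deaths, follow-up 4–28 months |
|---|---|---|---|
| 6 | 75% | 57% | 79% |
| 10 | 57% | 41% | 63% |
| 14 | 45% | 32% | 52% |

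The crude figure is below 12-month mortality in every row of the shorter window and above it in every row of the longer one.

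**6. Closure date alone.** Fix the true median at 12 months (12-month mortality 50%) and accrual at 24 months. Closing follow-up 0, 4, 12 or 24 months after the last entry gives crude deaths of 46, 57, 73 and 87%.

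**7. Kaplan-Meier in the same setting.** This was simulated with 1,500 replicates; 20, 40 or 80 patients; medians of 6, 12 and 18 months; closure 0, 4 or 24 months after last entry; and 1% random loss per month. Mean estimated 12-month survival stays within 0.5 percentage point of the truth throughout. The standard error is about 0.05–0.07 with 80 patients, 0.07–0.10 with 40 and 0.10–0.14 with 20. With closure at last entry and a true median of 18 months, the median is reached in 76% of runs with 80 patients and 59% with 20.

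**8. If survival follow-up is incomplete.** Assumed: 80 patients, closure 4 months after last entry, median 3 months to progression and a further 6 months to death. A given share of patients is censored 1 month after progression. True 12-month survival is about 0.44.

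| Share censored | Kaplan-Meier 12-month survival | Crude deaths |
|---|---|---|
| 0% | 0.438 | 65% |
| 25% | 0.464 | 51% |
| 50% | 0.505 | 37% |
| 100% | 0.768 | 10% |

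Both summaries are distorted.

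**The case against.** The change is openly listed with its reason. OS is unpowered and drives no decision. SAP section 6.4 calls its figure a number and percentage of deaths and does not offer it as 12-month mortality. Individual data and deaths are to be listed. All of that stands. It limits the consequences, but it does not give the percentage a follow-up time against which to read it.

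Protocol section 10.5.2 lets the sponsor replace secondary efficacy analyses with listings. That option applies if the primary endpoint is not met, and the SAP does not invoke it.

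The strongest objection is that limited follow-up may mean missing contacts as well as short ones. SAP section 3.2 counts the subjects who consented to survival follow-up, so coverage may be incomplete. Protocol section 7.1.4.3 also allowed that follow-up to be skipped if the primary endpoint failed. Kaplan-Meier would then be optimistic, as step 8 shows. This stands as a caveat. It does not favour the crude percentage, which the same gap pulls down.

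Two stronger readings are tempting. A reader might infer that the crude percentage understates mortality. Step 5 shows that either direction is possible, and the actual accrual and follow-up are not in the documents. A reader might also infer that the percentage alone blocks comparison with other studies. A pooled Kaplan-Meier curve from a single-arm cohort of mixed tumour types would have limited external comparability too.

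**Conclusion.** The point holds as a choice of analysis that should be changed. Early closure on a calendar date does not justify dropping Kaplan-Meier for OS, and the SAP accepts the method for PFS in the same terminated study. The crude percentage depends on accrual and closure date: in the illustrations it runs from 18 points below 12-month mortality (57 against 75%) to 37 points above it (87 against 50%). These sizes rest on exponential survival and uniform entry. The actual number of patients, deaths and follow-up times are not given, so neither the direction nor the size is known for this trial. The advantage of Kaplan-Meier rests on non-informative censoring.

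The conflict between protocol sections 10.4.4 and 10.5.2 is real but has no effect under the present SAP, which censors no OS times. It matters once Kaplan-Meier is restored. Tumour assessments are not collected after treatment, so for patients who stop without progression section 10.4.4 would discard later survival contacts. The primary analysis is unaffected.

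**What to change.** - In SAP sections 2, 2.1 and 6.4, restore the protocol's Kaplan-Meier OS on the full analysis set, censored at last contact as in protocol section 10.5.2.
- Delete OS from the censoring rule in protocol section 10.4.4, or state in the SAP that section 10.5.2 governs.
- Report 6- and 12-month rates with 95% confidence intervals, numbers at risk, the median or a statement that it was not reached, median follow-up, and reasons for censoring.
- Keep the number and percentage of deaths as a supplementary line.
- Add a caveat that the curve may be optimistic if patients without survival follow-up were censored around progression, and read it beside the consent count from SAP section 3.2.

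The cost is one table, one figure and some SAP wording. The dates of first dose, death and last contact are those that the protocol's own OS definition needs, and protocol section 7.1.4.3 sends survival information to the eCRFs. How complete they are should be checked. Intervals will be wide, which properly reflects the short follow-up.

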3.1 Analysis sets

The following analysis data sets will be used in the analyses:

Full analysis set (FAS): The FAS will include all subjects who have received at least one dose of the study drug. The FAS will be the primary set for efficacy analyses.

Safety set (SS): The SS will include all subjects who have received at least one dose of the study treatment and had at least one post-baseline safety assessment. A subjects who has received a dose of study treatment and who has no post-treatment safety data of any kind (i.e., no AE assessment, no vitals, no ECG, no cardiac imaging, no ECOG performance status, and no laboratory assessment) will be excluded from the SS. Note that the statement 'no adverse event' is considered as an assessment of AE.

